PROSPECTIVE ANALYSIS OF LOTEPREDNOL ETABONATE OPHTHALMIC SUSPENSION 0.25% FOR PREVENTION OF IMMUNOLOGIC REJECTION AFTER DESCEMET MEMBRANE ENDOTHELIAL KERATOPLASTY

NCT05136443

DOCUMENT DATE: NOVEMBER 3, 2021

- CLINICAL PROTOCOL -

PROSPECTIVE ANALYSIS OF LOTEPREDNOL ETABONATE OPHTHALMIC SUSPENSION 0.25% FOR PREVENTION OF IMMUNOLOGIC REJECTION AFTER DESCEMET MEMBRANE ENDOTHELIAL KERATOPLASTY

Protocol # 2021-002 Version Date 11/3/21

Principal Investigator and Sponsor

[name] MD [name]

[contact],

[contact]

1. Purpose of the Study and Background

1.1 Purpose of the Study:

The purpose of this study is to assess off-label use of loteprednol etabonate 0.25% ophthalmic suspension for prevention of immunologic rejection after Descemet membrane endothelial keratoplasty (DMEK).

1.2 Background

Topical corticosteroids have long been the mainstay for preventing and treating corneal graft rejection.[1] Typically, topical corticosteroids are dosed 4 times a day for several months, followed by tapered dosing for an extended period of time, sometimes indefinitely, after surgery.[1] If a patient experiences an immunologic graft rejection episode, corticosteroid use is increased in an effort to save the graft.

A number of side effects are associated with long-term corticosteroid use. In particular, up to one third of patients with no previous diagnosis of glaucoma experience intraocular pressure elevation with prolonged use of prednisolone acetate 0.1% ophthalmic suspension,[2] which is commonly used to prevent rejection following corneal transplantation.[1]

In our earlier studies, DMEK recipients used prednisolone acetate 1% four times daily for 1 month and then were randomized to a tapering dose of prednisolone acetate 1% ophthalmic suspension, fluorometholone 0.1% ophthalmic suspension, or loteprednol etabonate 0.5% gel. The loteprednol etabonate 0.5% gel and fluorometholone 0.1% suspension were as effective as prednisolone acetate 1% at preventing immunologic rejection episodes and were associated with significantly lower rates of steroid-induced ocular hypertension. [3,4]

This study will assess the use of a tapering dose of loteprednol etabonate 0.25% suspension from one month to one year after DMEK. The rates of immunologic rejection episodes and steroid-induced ocular hypertension will be compared with the respective rates observed in the earlier studies with use of prednisolone acetate 1% suspension, loteprednol etabonate 0.5% gel, or fluorometholone 0.1% suspension.

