3.0 Methods & Procedures

3.1 Study procedures and assessments.

- Screening: Prospective subjects, who have recently undergone DMEK, will be considered for entry into the study.
- Enrollment: Subjects meeting the inclusion and exclusion criteria will be informed of the opportunity to participate in the study. Subjects will be entered into the study after providing written informed consent. Each subject will be instructed that if they decide not to participate, they may withdraw at any time.
- Study Treatment Regimen: At one month after DMEK (or at the time of study enrollment if that is more than one month after DMEK) participants will discontinue use of the prednisolone acetate 1% ophthalmic suspension that was prescribed for use after

DMEK, and they will be provided with loteprednol etabonate 0.25% ophthalmic suspension for use 4 times daily for 2 months, 3 times daily for a month, twice daily for a month, then once daily until the 12-month postoperative exam.

• Rescue medication: if a study subject experiences inflammation or a questionable immunologic rejection episode in the study eye within the first month after enrollment, they will be instructed to use prednisolone acetate 1% ophthalmic suspension up to 8x/day for one week, 6x/day for 1 week, 4x/day for one week and 3x/day for one week). The study subject will then restart the study dosing schedule. The month of rescue treatment will allow those with greater than average inflammation to remain in the study by providing an additional month of increased steroid strength before resuming a weaker steroid regimen.

• Examinations:

- Schedule: Each subject will be examined at 1, 3, 6 and 12 months after DMEK as detailed in Table 1. The examination schedule and procedures are standard of care for DMEK patients.
- O Procedures: At each exam, medical and ophthalmic histories will be updated, adverse events will be recorded, and measurements of manifest refraction, visual acuity, corneal thickness (pachymetry) and intraocular pressure will be made. Corneal endothelial cell density will be measured by specular or confocal microscopy if possible. A slit lamp examination will be performed to assess the health of the transplant and document any conjunctival or lid hyperemia, stromal inflammation, superficial punctate keratitis, other surface toxicity of the cornea, neovascularization of the cornea, cells or flare in the anterior chamber, or evidence of transplant rejection.

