3.2 Data Analysis and Data Monitoring: The primary outcome measures are the incidence of clinically significant intraocular pressure (IOP) elevation (defined as IOP \geq 24mmHg or a relative increase over the pre-transplant IOP of \geq 10mmHg), and the incidence of initial allograft rejection episodes or necessity to increase corticosteroids

because of breakthrough corneal or anterior chamber inflammation. The data will be analyzed using Kaplan Meier survival analysis and the log rank test.

A statistical power analysis indicated that a sample size of 70 participants would provide 80% power to detect a statistically significant difference in the rate of IOP elevation between loteprednol etabonate 0.25% and prednisolone acetate 1%, based on observed rates of IOP elevation in an earlier study that compared loteprednol 0.5% gel with prednisolone 1% suspension.⁴

3.3 Data Storage and Confidentiality: Research data will be stored in a locked cabinet or locked room and on a password protected server to prevent unauthorized access to data. The investigators and research staff will have access to the data. Subject identifiers will be removed from study data released to the Sponsor or for publication.

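### The powered IOP comparison sets one treated cohort against eyes from earlier studies with an unadjusted log-rank test, so any cohort difference would be mixed with the drug effect

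*Combined protocol and SAP*

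**What the plan says.** Section 3.1 describes one regimen: at one month after DMEK, "or at the time of study enrollment if that is more than one month after DMEK", participants stop prednisolone acetate 1% and "they will be provided with loteprednol etabonate 0.25% ophthalmic suspension". Section 1.3 calls the study prospective and open-label. Neither randomisation nor a concurrent control is described.

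Section 1.2 supplies the comparator. This study's rates "will be compared with the respective rates observed in the earlier studies with use of prednisolone acetate 1% suspension", loteprednol 0.5% gel or fluorometholone 0.1%. On the source of those eyes it says: "In our earlier studies, DMEK recipients used prednisolone acetate 1% four times daily for 1 month and then were randomized" to one of the three regimens.

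Section 3.2 defines IOP elevation as a pressure of at least 24 mmHg or "a relative increase over the pre-transplant IOP of" at least 10 mmHg. The whole analysis statement is: "The data will be analyzed using Kaplan Meier survival analysis and the log rank test". The sample-size sentence says that 70 participants give "80% power to detect a statistically significant difference in the rate of IOP elevation between loteprednol etabonate 0.25% and prednisolone acetate 1" (the percent sign is cut), with rates taken from the study of loteprednol gel against prednisolone.

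The plan does not mention covariates, matching, weighting, a comparability check or a sensitivity analysis for the historical comparison. It does not say whether the prednisolone arm of the gel study is used alone or together with that of the fluorometholone study.

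**The concern.** Randomisation in the earlier studies protects comparisons among their own arms. It does not protect a comparison between those arms and a cohort recruited later. If the two sets of eyes differ in underlying risk of IOP elevation, an unadjusted log-rank test reads that difference as part of the treatment contrast, in either direction.

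IOP elevation is a primary outcome and the only one for which power is stated, so this p-value is likely to carry the main conclusion. The 80% power allows for sampling error and says nothing about bias between cohorts. As written, the plan gives no means of separating the two.

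**Working it through.** **Step 1: which test is planned.** There is one regimen (3.1), the comparison is with earlier-study rates (1.2), power is for a significant difference from prednisolone 1% (3.2), and log-rank is the only test named (3.2). A two-group log-rank test needs a second group, and only earlier-study eyes can supply one. This is inference. A one-sample version against a reference curve is also possible.

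**Step 2: the plan's own figure.** Section 3.2 gives 70 participants and 80% power, but no event rates, hazard ratio, alpha, sidedness or comparator size. The figure can be neither reproduced nor called wrong. For orientation, under an assumed 70 v 70 eyes and two-sided 5%, an exact calculation gives 80% power at 20 v 5.0%, 25 v 7.9% or 33.3 v 13.7%.

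**Step 3: effect of a cohort difference when the drug has none.** All inputs are assumptions: 70 current eyes; 35, 70 or 140 historical eyes; historical rate 20, 25 or 33.3%; two-sided 5% pooled score test for two proportions, standing in for log-rank at a fixed horizon. The only IOP rate printed is the background figure in 1.2 of up to one third. It is not stated to be the power input.

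The normal approximation to the chance of a significant result favouring loteprednol is 1 − Φ[(1.96·SE0 − d)/SE1]. For 25 v 20% and 70 v 70:

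- pooled rate = 0.225
- SE0 = √(0.225 × 0.775 × 2/70) = 0.0706
- SE1 = √(0.25 × 0.75/70 + 0.20 × 0.80/70) = 0.0705
- (1.96 × 0.0706 − 0.05)/0.0705 = 1.25, giving 0.105

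Exact enumeration gives 0.107 for this case. The full set of exact results:

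| Historical rate | Current eyes lower by | n = 35 | n = 70 | n = 140 |
|---|---|---|---|---|
| 20% | 0 | 0.030 | 0.025 | 0.023 |
| 20% | 2 points | 0.052 | 0.049 | 0.048 |
| 20% | 5 points | 0.108 | 0.118 | 0.129 |
| 25% | 0 | 0.029 | 0.026 | 0.023 |
| 25% | 2 points | 0.048 | 0.047 | 0.047 |
| 25% | 5 points | 0.097 | 0.107 | 0.116 |
| 33.3% | 0 | 0.027 | 0.025 | 0.024 |
| 33.3% | 2 points | 0.042 | 0.045 | 0.046 |
| 33.3% | 5 points | 0.080 | 0.095 | 0.107 |

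A simulated log-rank test for the 5-point cases (70 v 70, exponential times over 11 months, events seen at the 3-, 6- and 12-month visits, no dropout, 6,000 runs) gave 0.116, 0.099 and 0.096. With 25% in both cohorts it gave 0.024.

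**Step 4: the other direction.** Take the 80%-power alternatives in step 2, keep their odds ratios, and raise the current eyes' baseline risk by 5 points. At 70 v 70, power falls to 0.67, 0.66 and 0.65. Recalibrating the alternative to 80% at 35 or 140 historical eyes widens the range to 0.61-0.72.

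**Step 5: room for adjustment.** Expected events at the step 2 alternatives are 70 × (0.20 + 0.050) = 17.5, 70 × (0.25 + 0.079) ≈ 23.1 and 70 × (0.333 + 0.137) = 32.9. With treatment plus one covariate that is about 9, 12 and 16 events per parameter. With three covariates it is only 4 to 8. At a 10% historical rate (10 v 0.5%) there are about 7 events in all.

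**The case against.** A small open-label study may use historical controls, and this one says openly that it does. The controls are better than most: same team, same operation, one month of prednisolone 1% before the change of regimen, and a switch here between about one month and seven weeks. Primary open angle glaucoma is excluded, and the rise of at least 10 mmHg is measured against each eye's own pre-transplant pressure, which partly accounts for starting IOP. All of this stands. It lowers the risk without removing it: the 24 mmHg limb takes no account of starting pressure, no numeric IOP limit applies at entry, and nothing says the earlier eyes met the same exclusions.

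A reader might infer that the endpoint definitions differ, because section 1.2 says the earlier gel and fluorometholone arms "were associated with significantly lower rates of steroid-induced ocular hypertension" while section 3.2 gives numeric thresholds. The documents do not support that. Section 1.2 uses the same term for this study's outcome, and section 3.2 calls the earlier outcome IOP elevation. Whether the definitions match cannot be seen from here.

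It is also fair that no cohort difference of any size is documented. The 2- and 5-point scenarios show sensitivity and are not estimates. Section 3.2 does identify the gel study as the source of the power assumption, so the open question on the comparator is only whether the fluorometholone study's prednisolone arm is used as well. The reference number attached to that sentence belongs to the fluorometholone study in the reference list. That is a separate clerical slip and adds no weight.

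**Conclusion.** The concern holds in a limited form. Followed as written, the plan yields an unadjusted, non-randomised p-value for its powered comparison, with no stated alignment of the earlier eyes to this cohort. Under the assumptions in the working, the false favourable rate stays at about 2-3% if the cohorts match. It is about 4-5% with a 2-point difference in underlying risk and about 8-13% with a 5-point difference. A difference the other way costs power.

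The size and direction of any actual bias cannot be derived from the documents. A reader might conclude that the cohorts do differ, or that the comparison is invalid. Neither follows: the documents are silent on comparability, and the plan makes no explicit causal claim. This is a worthwhile, inexpensive improvement to section 3.2 and no reason to hold up the study.

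**What to change.** In section 3.2:

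1. State whether the comparator is the prednisolone arm of the gel study alone or also that of the fluorometholone study. Apply this study's IOP definition, its time origin (the switch) and those eligibility criteria that can be applied retrospectively to the earlier eyes. If both studies are used, show each separately.
2. Keep Kaplan-Meier and the log-rank test, and report the difference with a 95% CI. Add one prespecified analysis adjusted for 1-month IOP, which is already in Table 1, or for pre-transplant IOP, which the endpoint requires but Table 1 does not list. Penalise the model if events are few.
3. If patient-level data cannot be retrieved, report this study's Kaplan-Meier rate with a 95% CI beside the historical rates, and base no drug-difference claim on a p-value.

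The cost is retrieving data from the earlier studies, whose availability is not stated, and one extra analysis. No new patients or procedures are needed. The downsides are a possibly wider interval, few events for adjustment, and unmeasured differences between studies that no adjustment will remove.

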1.3 Study Design

- Prospective, open-label clinical study
- Main Outcome Measures
 - o Rate of intraocular pressure elevation
 - o Rate of initial immunologic graft rejection episodes

2.0 Characteristics of the Research Population

- 2.1 **Number of Subjects:** up to 75 DMEK recipients may enroll 1 eye into the study at the 1-month postoperative exam.
- 2.2 **Gender of Subjects:** both men and women will be enrolled
- 2.3 **Age of Subjects:** 18-90 years of age. The rationale for not including minors is that DMEK is performed to treat endothelial dysfunction, a condition usually seen in adults over 40 years of age.
- 2.4 Racial and Ethnic Origin: Subjects may be of any racial or ethnic origin.
- 2.5 **Inclusion criteria:** the following are requirements for study inclusion:
 - o At least 18 years of age
 - o Male or female patient who had DMEK within the past 1 to 7 weeks.
 - o Patient is able and willing to administer eye drops.
 - o Patient is able to comprehend and has signed the Informed Consent form.
 - o Patient is likely to complete the 11-month study duration.

2.6: Exclusion criteria:

- o A history of a previous rejection episode in the study eye
- o A patient exhibiting intraocular inflammation.
- A patient with a known sensitivity to any of the ingredients in the study medications
- A patient who has a condition (i.e., UNCONTROLLED systemic disease) or is in a situation which in the investigator's opinion may put the patient at significant risk, may confound the study results, or may interfere significantly with the patient's participation in the study
- o A patient with abnormal eyelid function.
- A patient that is exhibiting active corneal ulceration, keratitis, or conjunctivitis, or who has a history of herpetic keratitis.
- o A patient with primary open angle glaucoma.
- Presence of any ocular disease that would interfere with the evaluation of the study treatment. However, patients with a history of cystoid macular edema, age-related macular degeneration, corneal neovascularization, and other non-interfering comorbidities may be enrolled.

- A patient with a history of non-compliance with using prescribed medication.
- Patients who are pregnant or planning to become pregnant within the duration of the study

2.7 Vulnerable Subjects: No potentially vulnerable subjects will be enrolled because there may be no direct benefit to the patient; rather, important knowledge which may benefit future subjects is being sought. As such, the direct benefit would not outweigh risks for vulnerable populations.

Minors will not be enrolled into this study because the conditions being studied under this protocol are not typical problems for minors. Endothelial keratoplasty is performed to treat endothelial dysfunction, a condition usually seen only in older (>40 years of age) adults.)

Pregnant women will not be enrolled into this study as potential risks and harm to the fetus is unknown.

This study plans to exclude any person who does not speak English as non-English speaking patients are not normally seen at the study site so a translator would not be available to translate the consent form into the patient's native language.

3.0 Methods & Procedures

3.1 Study procedures and assessments.

- Screening: Prospective subjects, who have recently undergone DMEK, will be considered for entry into the study.
- Enrollment: Subjects meeting the inclusion and exclusion criteria will be informed of the opportunity to participate in the study. Subjects will be entered into the study after providing written informed consent. Each subject will be instructed that if they decide not to participate, they may withdraw at any time.
- Study Treatment Regimen: At one month after DMEK (or at the time of study enrollment if that is more than one month after DMEK) participants will discontinue use of the prednisolone acetate 1% ophthalmic suspension that was prescribed for use after

DMEK, and they will be provided with loteprednol etabonate 0.25% ophthalmic suspension for use 4 times daily for 2 months, 3 times daily for a month, twice daily for a month, then once daily until the 12-month postoperative exam.

• Rescue medication: if a study subject experiences inflammation or a questionable immunologic rejection episode in the study eye within the first month after enrollment, they will be instructed to use prednisolone acetate 1% ophthalmic suspension up to 8x/day for one week, 6x/day for 1 week, 4x/day for one week and 3x/day for one week). The study subject will then restart the study dosing schedule. The month of rescue treatment will allow those with greater than average inflammation to remain in the study by providing an additional month of increased steroid strength before resuming a weaker steroid regimen.

• Examinations:

- Schedule: Each subject will be examined at 1, 3, 6 and 12 months after DMEK as detailed in Table 1. The examination schedule and procedures are standard of care for DMEK patients.
- O Procedures: At each exam, medical and ophthalmic histories will be updated, adverse events will be recorded, and measurements of manifest refraction, visual acuity, corneal thickness (pachymetry) and intraocular pressure will be made. Corneal endothelial cell density will be measured by specular or confocal microscopy if possible. A slit lamp examination will be performed to assess the health of the transplant and document any conjunctival or lid hyperemia, stromal inflammation, superficial punctate keratitis, other surface toxicity of the cornea, neovascularization of the cornea, cells or flare in the anterior chamber, or evidence of transplant rejection.
- Records release: Subjects may be asked to sign a records release form in case the subject_sees another eye specialist while enrolled in the study. This will allow the investigator to determine if there is a rejection episode or elevated intraocular pressure at examinations made with other physicians. Since the primary and secondary outcome measures (slit lamp examination for evidence of rejection and intraocular pressure measurement) are routine ophthalmic exams, the subject may have some of the exams performed by a local eye doctor if getting back to the study site is too burdensome.

- O Unscheduled examinations: Subjects will be instructed to return for extra examinations if they note any problems with the eye or any early signs of a possible rejection episode, such as a change in vision, redness to the eye, increased light sensitivity, burning sensation, or foreign body sensation.
- o Study completion: Subjects will be considered to have completed the study after they complete the one-year postoperative examination.
- Subject withdrawal or discontinuation: Each subject may voluntarily discontinue the study at any time they choose. Subjects who cannot complete the study for administrative reasons (e.g., non-compliance, failure to meet visit schedule, etc.) will be discontinued from the study. Discontinued subjects may be replaced. For subjects withdrawn from the study, the same measurements and assessments should be performed as done at one year. Adverse events should be followed up until resolution or stabilization of the adverse event.

Table 1

| | Screening | 3 months | 6 months | One year |
|--------------------------|-------------|------------|----------|----------|
| | (∼1 month | after DMEK | after | after |
| | after DMEK) | | DMEK | DMEK |
| Informed Consent | X | | | |
| Inclusion/Exclusion | X | | | |
| Criteria | | | | |
| Medical and | X | X | X | X |
| ophthalmic history | | | | |
| Adverse Events | | X | X | X |
| Uncorrected visual | X | X | X | X |
| acuity (Snellen) | | | | |
| Corrected Distance | X | X | X | X |
| visual acuity (Snellen) | | | | |
| Manifest refraction | X | X | X | X |
| Endothelial cell density | X | X | X | X |
| (if possible) | | | | |
| Intraocular Pressure | X | X | X | X |
| Ultrasonic Pachymetry | X | X | X | X |

3.2 Data Analysis and Data Monitoring: The primary outcome measures are the incidence of clinically significant intraocular pressure (IOP) elevation (defined as IOP \geq 24mmHg or a relative increase over the pre-transplant IOP of \geq 10mmHg), and the incidence of initial allograft rejection episodes or necessity to increase corticosteroids

because of breakthrough corneal or anterior chamber inflammation. The data will be analyzed using Kaplan Meier survival analysis and the log rank test.

A statistical power analysis indicated that a sample size of 70 participants would provide 80% power to detect a statistically significant difference in the rate of IOP elevation between loteprednol etabonate 0.25% and prednisolone acetate 1%, based on observed rates of IOP elevation in an earlier study that compared loteprednol 0.5% gel with prednisolone 1% suspension.⁴

3.3 Data Storage and Confidentiality: Research data will be stored in a locked cabinet or locked room and on a password protected server to prevent unauthorized access to data. The investigators and research staff will have access to the data. Subject identifiers will be removed from study data released to the Sponsor or for publication.

